Continuous variables were presented in median (range) while categorical data was expressed in frequency (%). A variable was considered as normally distributed when the Z-score was within ± 3.29 ($n \geq 50$). To compare the means/medians between two groups, independent samples t-test/Mann Whitney U test was used. To test the association between categorical variables, Chi square tests or Fisher exact test was used. Event free survival was calculated for the patients using the Kaplan-Meier survival plots using Log rank test and Breslow test. Univariate and multivariate Cox regression analysis were used to identify the predictors of survival. Variables found significant in Univariate analysis were included for multivariate analysis. A two tailed p-value of < 0.05 was considered statistically significant. Statistical package for social sciences version-23 (SPSS-23, IBM, Chicago, USA) and MedCals software was used for data analysis.

RESULTS:

During the study period, 48 participants {11 (22.9%) in Group 'E', 31 (64.5%) in Group 'I' and 6 (12.5%) in Group 'L'} underwent re-resection with curative intent. The demographic profile (age and gender), co-morbidities, tumor characteristics, extent of resection, resection margin and nodal clearance were similar in the three groups (each $p > 0.05$). Median age of participants with IGBC was 55 years and 2.7 times more common among females.

Similarly, presence of residual disease, grades of the tumor, primary stage of the tumor following index cholecystectomy, final stage after curative resection, adjuvant therapy and associated morbidity were statistically equal among the groups (each $p > 0.05$). No post operative mortality was recorded. The most common complication in the postoperative period was surgical site infection (SSI), recorded in 8 patients. Three patients required postoperative percutaneous drainage for intra-abdominal collection. No patient required prolonged hospital stay or reoperation.

Overall Survival (OS) and Disease-free survival (DFS):

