Mean and median follow-up was 51.6 and 40.6 months, respectively (range: 1.2-130.6). Total 9(18.7%) patients were reported lost to follow up during the study period. Mean overall survival (OS) in study patients was 91.75(95% CI: 8.32-75.44) months. As OS percentage did not reach <50%, resultant median survival could not be computed. Similarly the mean DFS following curative resection was 85.63 (95% CI: 69.48-101.79) months (As the patient recurrence free survival percentage did not reach below 50%, resultant median recurrence free survival time could not be computed).

In present study, 29(60.4%) of those undergoing definitive surgery received chemotherapy. Around 58% received >1 cycle and 44% could complete their therapy. Radiotherapy was given to 42% participants. The most important indications for adjuvant therapy included good performance status with advanced stage and margin positive and/or node positive disease. OS among participants who received adjuvant therapy was similar to those who were not offered chemotherapy [88.10 (95% CI: 67.18-109.03) Vs 87.56 (95% CI: 61.66-113.45) months (p=0.916) (Fig 1). Similarly DFS among participants who received adjuvant therapy was similar to those who did not receive any post operative treatment. [86.18 (95% CI: 65.73-106.64) Vs 85.37 (95% CI: 59.82-110.91) months (p=0.915).

[figure not shown]

Figure 1: Overall impact of adjuvant therapy on event free survival.

[figure not shown]

Figure 2 : Overall event free survival in study patients as per timing of treatment.

Kaplan Meier method (log rank test) was used to compare the event free and disease-free survival time of the patients among the three groups. Though the participants operated within 4 weeks and between 4-12 weeks fared a better OS and DFS than those operated beyond 12 weeks, the difference could not achieve statistical significance. (Event free survival time (p=0.575) and

disease-free survival time (p=0.581))(Figures 2&3)

[figure not shown]

Figure 3: Overall disease free survival in study patients as per timing of treatment.

Survival Analysis:

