On Univariate analysis of factors associated with significantly poor survival following curative resection were: presence of nodal metastasis, poor differentiation and lesions necessitating CBD excision. Other factors portending an unfavorable outcome included presence of residual disease, lympho-vascular invasion and delay in re-resection beyond 12 weeks, though the difference was not statistically significant. Primary tumor stage, resection margin and use of adjuvant therapy did not affect the overall survival (each $p > 0.05$). Residual disease was present in 20 out of 48 (41.6%) participants. The distribution of residual disease following re-resection, according to the index T-stage was (16% in T1, 29% in T2 and 72% in T3 tumors).

To further assess the predictors of survival among the participants, multivariate Cox regression analysis was used. Three variables (Node status, Grades and Extent of resection) which were significant on Univariate analysis were included in multivariate analysis. Results showed that disease grade was the only significant independent predictor of survival. Presence of positive

nodes ($p=0.052$) and the need for CBD excision (0.133) was associated with increased relative risk of disease related mortality, although the difference was not statistically significant.

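### With only 6 Late patients, p>0.05 does not show that the three timing groups were equal; the comparability statement is unsupported

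*Combined protocol and SAP*

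**What the plan says.** The Statistical Analysis section says that for associations between categorical variables "Chi square tests or Fisher exact test was used", two-sided at 0.05. It gives no equivalence margin and no power calculation.

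RESULTS splits the 48 re-resected patients into Early 11, Intermediate 31 and Late 6, and makes two comparability statements, each resting on p>0.05:

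- The first paragraph covers demographics, co-morbidities and tumour characteristics, and adds that "extent of resection, resection margin and nodal clearance were similar in the three groups".
- The second lists "presence of residual disease, grades of the tumor, primary stage of the tumor following index cholecystectomy, final stage after curative resection" and ends "adjuvant therapy and associated morbidity were statistically equal among the groups".

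No counts by group and no intervals for between-group differences are given. The one relevant total is in Survival Analysis: "Residual disease was present in 20 out of 48 (41.6%) participants".

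On the timing result, the survival section reports log-rank p=0.575 and p=0.581 and says that patients operated on earlier "fared a better OS and DFS than those operated beyond 12 weeks, the difference could not achieve statistical significance". Survival Analysis names the univariately significant factors as "presence of nodal metastasis, poor differentiation and lesions necessitating CBD excision", and describes the multivariate model thus: "Three variables (Node status, Grades and Extent of resection) which were significant on Univariate analysis were included in multivariate analysis". Timing is not in that model.

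**The concern.** Failure to reject equality is reported as equality. A test with 6 patients in one group can miss large differences, so p>0.05 is compatible with groups that are alike and with groups that are far apart.

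The time gap between index surgery and re-resection is part of the primary objective in the Study Plan. Its survival comparison is an unadjusted log-rank test, and no estimate of the timing effect is adjusted for any other factor. A reader will therefore lean on the comparability statement when judging whether confounding could have shaped the timing result. Grade is among the factors called equal. It was significant on univariate analysis and was the only independent predictor in the multivariate model. More poorly differentiated tumours in Late would make delay look worse than it is; fewer would mask an effect of delay. The p-values exclude neither.

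**Working it through.** **Inputs.** Group sizes 11, 31 and 6 (RESULTS); residual disease 20 of 48 (Survival Analysis); two-sided 0.05, chi-square or Fisher (Statistical Analysis). The totals check: 11 + 31 + 6 = 48 and 20/48 = 41.67%, printed as 41.6%. The document gives only p>0.05 for the comparison by group, so there is no exact p-value to reproduce. The question is which Late counts are compatible with p>0.05.

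**Three-group tests.** Let a, b and c be the residual-disease counts in Early, Intermediate and Late, with a + b + c = 20.

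- Exact test (Fisher-Freeman-Halton): P(a,b,c) = C(11,a)·C(31,b)·C(6,c)/C(48,20). The p-value is the sum of P over all tables no more probable than the one in hand.
- Pearson chi-square, 2 df. The expected counts with residual disease are 11×20/48 = 4.58, 31×20/48 = 12.92 and 6×20/48 = 2.50.

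All possible tables were enumerated. The last column compares Late with the other 42.

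| Late | Early counts with exact p>0.05 | Early counts with chi-square p>0.05 | Largest exact p | Late vs rest: Fisher / uncorrected chi-square |
|---|---|---|---|---|
| 0/6 | 4–6 | 4–6 | 0.093 | 0.034 / 0.027 |
| 1/6 | 2–7 | 3–7 | 0.475 | 0.379 / 0.184 |
| 2/6 | 2–8 | 2–8 | 1.000 | 1.000 / 0.658 |
| 3/6 | 2–7 | 2–7 | 0.915 | 0.683 / 0.658 |
| 4/6 | 2–7 | 2–7 | 0.431 | 0.218 / 0.184 |
| 5/6 | 3–5 | 3–5 | 0.111 | 0.069 / 0.027 |
| 6/6 | none | none | 0.008 | 0.003 / 0.002 |

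For 1/6 to 4/6, the Early counts that pass both three-group tests throughout are 3 to 7. Two examples:

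- 5/11, 14/31, 1/6: exact p=0.475; chi-square = 1.76, p=0.414.
- 4/11, 12/31, 4/6: exact p=0.431; chi-square = 1.78, p=0.410.

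**Size of the differences that pass.** Late minus the other 42, with the Newcombe interval built from Wilson limits (l, u). Lower limit: d − √[(p1−l1)² + (u2−p2)²]. Upper limit: d + √[(u1−p1)² + (p2−l2)²].

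- Late 1/6 vs 19/42: d = 0.1667 − 0.4524 = −0.2857. Wilson limits are 0.0301 to 0.5635 and 0.3122 to 0.6005. Lower: −0.2857 − √(0.1366² + 0.1481²) = −0.487. Upper: −0.2857 + √(0.3968² + 0.1402²) = +0.135.
- Late 4/6 vs 16/42: d = 0.6667 − 0.3810 = +0.2857. Wilson limits are 0.3000 to 0.9032 and 0.2500 to 0.5319. Lower: 0.2857 − √(0.3667² + 0.1509²) = −0.111. Upper: 0.2857 + √(0.2365² + 0.1310²) = +0.556.

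**Power.** If the true Late rate were 1/6 and the other two groups 45%, the three-group exact test would have about 15% power. With Late at 4/6 and the others at 38%, it would have about 20%.

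**Grade (assumed totals).** The number with poor differentiation is not given. Treating it as yes/no, for any assumed total from 14 to 34 of 48 the Late-vs-rest Fisher test leaves p>0.05 at a difference of at least 38 points in one direction. For totals from 12 to 36 it does so at 28.6 points or more.

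**The case against.** The strongest objection concerns causal order. Residual disease and final stage are found at re-resection, and adjuvant therapy and morbidity come later still. If delay allows progression, an excess of residual disease in Late is part of the effect of delay, not a bias in it. This stands. A reader might infer that every factor in the two lists is a potential confounder; the document does not support that. The confounding argument applies to factors fixed before the interval, such as grade and index T stage, which the Study Plan says were documented from the index specimen in most cases.

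Second, the only calculation resting wholly on reported figures is for residual disease, which Survival Analysis reports as not significantly associated with survival. That also stands. The example shows what p>0.05 can hide with these group sizes; carrying it over to grade needs an assumed total.

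Third, the document never says that the timing comparison is unconfounded. It shows p>0.05 beside the claim and reports the timing result cautiously. Nor is the comparability statement the only text bearing on confounding: Survival Analysis reports which factors were associated with survival, and timing was left out of the Cox model under the stated rule that only univariately significant variables enter. These points limit the consequence, but they do not make the equality claim correct.

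Fourth, the intervals are for Late against the rest, while the document's claim concerns three groups. That is so, which is why the range of passing counts is stated on the three-group tests.

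**Conclusion.** The claim of equality is unsupported as written. With 20 of 48 fixed, a Late residual-disease rate anywhere from 17% (1/6) to 67% (4/6) gives the same p>0.05, provided Early has 3 to 7 cases. The ends are narrower: 0/6 passes the three-group tests only with 4 to 6 Early cases, 5/6 only with 3 to 5, and 6/6 never passes.

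A reader might infer that the groups were imbalanced, or that the timing result is biased. Neither follows. Counts by group are not given, and the tables above are compatible with the report, not observed. No reported p-value changes. What changes is the conclusion about comparability: on factors fixed before the interval, grade above all, it is not established, so the unadjusted timing comparison cannot be assumed free of confounding.

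**What to change.** 1. In both RESULTS paragraphs, replace *similar* and *statistically equal* with a statement that no significant difference was detected.
2. Add one table of counts by group for each factor, with Late-minus-rest differences and 95% CIs.
3. Divide that table in two. Factors fixed before the interval: demographics, grade and index T stage. Factors found at or after re-resection: residual disease, nodal status, final stage, extent of resection, margin, adjuvant therapy and morbidity. Note that the second set may be consequences of delay rather than confounders.
4. State that, with 6 Late patients, comparability on the first set is not established, so the unadjusted timing comparison cannot be assumed free of confounding.

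The cost is a few sentences and one table from data already held, with no new data and no change to any reported test. The downside is that the intervals will be wide and will show how little 6 patients can say.

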Tumors were staged as per 8th edition of AJCC-TNM staging. Preoperative workup included contrast enhanced axial imaging (CECT – contrast enhanced computed tomography). In few cases with high risk features (residual disease on CT scan or late presentation), Positron Emission Tomography (PET) scan was added. Participants found fit for surgery and those with resectable disease on imaging were considered for the definite procedure. Laparoscopy was done preferably in those presenting beyond 4 weeks of index surgery or residual disease (local or nodal) on imaging to rule out metastasis. In absence of obvious distant metastasis (ascites, peritoneal nodules, mesenteric nodules, serosal nodules), inter-aortocaval (IAC) tissue was sent for evaluation of nodal metastasis. Once IAC node was found negative for deposits on frozen-section examination, radical re-resection was attempted. It included wedge resection of liver or Segment 4b/5 excision with regional lymphadenectomy. Extrahepatic bile duct excision was added in presence of positive cystic duct margin or direct invasion into the duct.

All available histopathology blocks and slides following the index cholecystectomy were re-reviewed by the pathologists at our institute. Tumor type, differentiation and primary T stage were documented for majority of cases. Interval between index cholecystectomy and date of re-operation was calculated for all the participants and divided into 3 groups: Early (<4weeks),

Intermediate (4-12 weeks) and Late (>12 weeks). Primary objective was to assess the effect of tumor characteristics and the time gap (between index surgery and re-resection) on overall survival following curative (R0/R1) resection.

Statistical Analysis:

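### The 95% confidence interval printed for mean overall survival (8.32-75.44 months) excludes its own estimate of 91.75; the two limits are almost certainly the standard error and the lower limit.

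*Combined protocol and SAP*

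**What the plan says.** The study plan makes overall survival the outcome of interest: "Primary objective was to assess the effect of tumor characteristics and the time gap (between index surgery and re-resection) on overall survival". The cohort is given in the Results: "During the study period, 48 participants" had re-resection with curative intent.

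Under the Results heading on overall and disease-free survival, the whole-cohort figure is: "Mean overall survival (OS) in study patients was 91.75(95% CI: 8.32-75.44) months". The same paragraph explains that the median could not be computed because the survival curve did not fall below 50%.

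The section gives five other mean survival times with 95% intervals:

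- Whole-cohort disease-free survival: "mean DFS following curative resection was 85.63 (95% CI: 69.48-101.79) months".
- Overall survival with and without adjuvant therapy: "88.10 (95% CI: 67.18-109.03) Vs 87.56 (95% CI: 61.66-113.45) months (p=0.916".
- Disease-free survival with and without adjuvant therapy: "86.18 (95% CI: 65.73-106.64) Vs 85.37 (95% CI: 59.82-110.91) months (p=0.915".

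No standard error is labelled anywhere, and no other part of the document gives a second interval for whole-cohort overall survival.

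**The concern.** A confidence interval built as estimate ± z × standard error must contain its estimate. This one does not: both printed limits are below 91.75. The sentence is ordinary running text with no redaction and no table to break, so nothing suggests a fault in extraction.

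With the median not reached, this mean and its interval are all a reader has for overall survival in the full cohort. Read literally, the lower limit is about 8 months. Anyone who extracts the interval for comparison or pooling, and derives a standard error from its width, gets about 17.1 months, roughly twice the value the figures support.

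**Working it through.** **Inputs**, all from the Results section on overall and disease-free survival: mean overall survival 91.75; printed limits 8.32 and 75.44; the five comparator estimates and intervals. The intervals are labelled 95%, so z = 1.96 (1.95996 unrounded).

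**Step 1. Take the printed pair as a confidence interval.**

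- Midpoint: (8.32 + 75.44)/2 = 41.88, against an estimate of 91.75.
- Half-width: (75.44 - 8.32)/2 = 33.56, which implies a standard error of 33.56/1.96 = 17.1.
- Gap between upper limit and estimate: 91.75 - 75.44 = 16.31 months.

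The printed interval is not reproduced.

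**Step 2. Check what form of interval the section uses elsewhere.**

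| Estimate | Printed 95% CI | Estimate - lower | Upper - estimate | Implied SE |
|---|---|---|---|---|
| DFS, all: 85.63 | 69.48-101.79 | 16.15 | 16.16 | 8.24 |
| OS, adjuvant: 88.10 | 67.18-109.03 | 20.92 | 20.93 | 10.68 |
| OS, no adjuvant: 87.56 | 61.66-113.45 | 25.90 | 25.89 | 13.21 |
| DFS, adjuvant: 86.18 | 65.73-106.64 | 20.45 | 20.46 | 10.44 |
| DFS, no adjuvant: 85.37 | 59.82-110.91 | 25.55 | 25.54 | 13.03 |

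All five contain their estimate, and the two half-widths differ by 0.01 month, which is rounding. The section therefore uses estimate ± z × SE.

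**Step 3. Take the printed pair as (standard error, lower limit).**

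- Forward: 91.75 - 1.96 × 8.32 = 75.44, the second printed number.
- Backward: (91.75 - 75.44)/1.96 = 8.32, the first printed number.
- Missing upper limit: 91.75 + 1.96 × 8.32 = 108.06.

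Allowing for rounding of the inputs (mean 91.745 to 91.755, SE 8.315 to 8.325), the lower limit lies between 75.43 and 75.46 and the upper between 108.04 and 108.07.

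**Step 4. Check plausibility.** An SE of 8.32 is close to the 8.24 implied by the disease-free survival interval for the whole cohort. The resulting upper limit of 108.06 is below the longest follow-up reported, 130.6 months.

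**Step 5. Compare the printed and implied intervals.**

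| | Printed | Implied | Difference |
|---|---|---|---|
| Lower limit | 8.32 | 75.44 | 67.12 |
| Upper limit | 75.44 | 108.06 | 32.62 |
| Width | 67.12 | 32.62 | 34.50 |
| Midpoint | 41.88 | 91.75 | 49.87 |

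**The case against.** The other side can fairly say four things.

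1. **The cause is inferred.** The document never calls 8.32 a standard error, so the corrected limits are inferred too. That is true. What is certain from the print is that the interval excludes its estimate. The two-decimal match in both directions makes the explanation close to conclusive, but it still has to be confirmed from the output.
2. **The figure is descriptive.** The primary objective concerns the effect of tumour characteristics and timing on survival. It is addressed by the comparison of the three timing groups (p=0.575) and the Cox models, neither of which uses this interval. This also stands, and it limits the consequence.
3. **The misprint is visible.** A careful reader would not believe a lower limit of 8 months beside a mean of 91.75. That lowers the risk of being misled, but it does not supply the correct interval. The coherent intervals by adjuvant therapy describe subgroups and do not replace a whole-cohort estimate.
4. **Symmetry does not prove the other figures correct.** It shows only that they are internally coherent. The whole-cohort mean overall survival (91.75) exceeds both adjuvant-therapy means (88.10 and 87.56), whereas whole-cohort disease-free survival (85.63) lies between its two (85.37 and 86.18). Means restricted to different times could produce this, so it does not show that 91.75 is wrong. It is a reason to check the point estimate along with the interval.

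**Conclusion.** The concern holds. The interval printed for whole-cohort mean overall survival is impossible as stated. If 8.32 is the standard error and the interval is the symmetric normal form used for the other five, the correct 95% interval is 75.44 to 108.06 months. The printed lower limit is then too low by 67.12 months, the printed upper limit is too low by 32.62 months, and the printed width is about twice what it should be.

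This is a reporting error in one line. It must be corrected because it affects the only whole-cohort summary of overall survival. It does not alter the log-rank p-values, the Cox results or the study's conclusions.

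**What to change.** Retrieve the survival output and confirm the mean, its standard error and both limits. If they agree with the working above, report mean overall survival as 91.75 months (SE 8.32; 95% CI 75.44-108.06). If they do not, print what the output gives.

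In the same edit, state the follow-up time to which each mean is restricted. A Kaplan-Meier mean depends on that time when the curve has not reached zero, and stating it would let a reader judge why the whole-cohort mean exceeds both adjuvant-therapy means.

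The cost is one corrected line and a short note on restriction time. It needs no new data and no change to the other analyses.

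### Mean OS and DFS in months are restricted means with no stated cut-off, and the overall OS line reconciles neither with the adjuvant subgroup means nor with its own confidence interval.

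*Combined protocol and SAP*

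**What the plan says.** All the survival figures at issue are in the combined protocol and SAP, under Results, Overall Survival (OS) and Disease-free survival (DFS).

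- Overall OS: "Mean overall survival (OS) in study patients was 91.75" months. With its interval, the sentence reads: "Mean overall survival (OS) in study patients was 91.75(95% CI: 8.32-75.44) months".
- Why there is no median: "As OS percentage did not reach <50%, resultant median survival could not be computed". The same explanation is given for DFS, whose mean is 85.63 months (95% CI 69.48-101.79).
- Follow-up: "Mean and median follow-up was 51.6 and 40.6 months, respectively (range: 1.2-130.6" months). On losses: "Total 9(18.7%) patients were reported lost to follow up during the study period".
- Adjuvant therapy against none, OS: "88.10 (95% CI: 67.18-109.03) Vs 87.56 (95% CI: 61.66-113.45) months (p=0.916"). The corresponding DFS means are 86.18 (65.73-106.64) and 85.37 (59.82-110.91) months, p=0.915.
- Group size: "29(60.4%) of those undergoing definitive surgery received chemotherapy", out of the 48 re-resected. The sizes of the two groups compared are not printed.

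The Statistical Analysis section names Kaplan-Meier plots with log-rank and Breslow tests, and Cox regression. It does not mention a restricted mean or a truncation time. The text gives no survival percentage at any fixed time. Figures 1 to 3 are survival plots that are not available in this copy.

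**The concern.** When a survival curve ends well above zero, the Kaplan-Meier mean depends on where the area is cut off as well as on the curve. Unless the cut-off is stated, the number cannot be interpreted or compared with another series. A reader may take about 92 months as expected survival after re-resection. In fact it partly reflects a cohort treated from 2009 to 2018 with follow-up to December 2019. With median follow-up of 40.6 months, much of the area out to 130.6 months rests on few patients.

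The same doubt applies to the adjuvant comparison, where two means are set side by side without a stated common time base.

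A second and separate problem is that the OS figures do not agree with one another. The overall mean is higher than both subgroup means, and the overall interval does not contain its own point estimate. At stake is whether the descriptive survival results can be trusted as printed.

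**Working it through.** **Inputs (Results, OS and DFS subsection).** Overall OS 91.75 (8.32-75.44); overall DFS 85.63; adjuvant and no-adjuvant OS 88.10 and 87.56; the same for DFS 86.18 and 85.37; longest follow-up 130.6 months; 48 patients, 29 given chemotherapy. The split 29:19 (48 - 29 = 19) is an assumption. The means themselves cannot be rebuilt without patient data.

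**1. The printed OS interval.** With a Wald interval, mean ± 1.96 × SE, try SE = 8.32:
- lower: 91.75 - 1.96 × 8.32 = 75.44, exactly the printed second limit;
- upper: 91.75 + 1.96 × 8.32 = 108.06, which is not printed.

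So 8.32 appears to be the SE, 75.44 the lower limit, and the upper limit is missing. The other five-figure sets are sound: for overall DFS, (69.48 + 101.79)/2 = 85.635 against 85.63, and the four subgroup means also equal their interval midpoints to within 0.01.

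**2. The means are restricted.** If the OS curve stays at or above 50% up to 130.6 months, the area to that point is at least 0.5 × 130.6 = 65.3 months. A mean of 91.75 corresponds to average survival of 91.75/130.6 = 70% over the window. Nothing is known of the curve beyond it.

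**3. How much the cut-off matters.** Assume S(t) = p + (1 - p)exp(-ht), with plateau p from 0.50 to 0.65, and choose h so that the area to an assumed 130.6 months is 91.75. The area to T is pT + (1 - p)(1 - exp(-hT))/h.

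| p | h per month | area to 60 | area to 120 | S(130.6) |
|---|---|---|---|---|
| 0.50 | 0.0168 | 48.9 | 85.8 | 0.556 |
| 0.55 | 0.0212 | 48.3 | 85.6 | 0.578 |
| 0.60 | 0.0292 | 47.3 | 85.3 | 0.609 |
| 0.65 | 0.0510 | 45.6 | 84.9 | 0.650 |

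All four respect the stated 50% floor. The same curve gives about 46-49 months at a 60-month cut-off and about 85-86 at 120.

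**4. Do the means reconcile?**
- OS: (29 × 88.10 + 19 × 87.56)/48 = 87.89. The overall mean is 91.75 - 87.89 = 3.86 months above this, and 91.75 - 88.10 = 3.65 above the higher subgroup. Whatever the split, the weighted average cannot exceed 88.10.
- DFS: (29 × 86.18 + 19 × 85.37)/48 = 85.86. The overall 85.63 lies between the two subgroup means.
- OS minus DFS: overall 91.75 - 85.63 = 6.12; adjuvant 88.10 - 86.18 = 1.92; no adjuvant 87.56 - 85.37 = 2.19.

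**5. Could separate horizons explain it?** With the overall curve cut at 130.6 and an assumed late survival of 0.5-0.7, a 3.86-month gap needs one subgroup to end early. For the no-adjuvant group: 130.6 - 3.86/(19/48)/0.5 = 111 months, or 117 with 0.7. For the adjuvant group the figures are 118 and 121. So for OS alone it is possible.

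In simulated cohorts of 29 and 19 with no true difference (assumed 55% long-term survivors, 12-132 months of potential follow-up, 9 in 48 lost early), the overall mean exceeded both subgroup means by more than 3 months in about 5% of runs with separate horizons. With a common horizon it did so in about 0.02%. When OS and DFS share the same censoring, as they normally would, an OS excess above 3 months without a DFS excess occurred in only about 0.15% to 0.3% of runs. These rates depend on the assumptions.

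**The case against.** The strongest defence is that no inferential conclusion depends on these means. The primary objective concerns tumour characteristics and timing. Timing was compared by log rank (p=0.575 and 0.581), predictors by Cox regression, and no mean is reported for any timing group. Neither method uses the means. The test behind the adjuvant p-values is not named beside them, but if it is one of the planned tests the same applies. This stands: the fault lies in description, and no reported test is shown to change. Fixed-time percentages or numbers at risk may also appear in the figures, which cannot be checked here.

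Several stronger readings are tempting, and the documents do not support them:

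- **That unequal horizons explain the OS mismatch.** They could for OS alone, but the DFS means do not show the pattern, and the OS-DFS gap of 6.12 months overall against 1.92 and 2.19 argues against horizons alone.
- **That an overall mean above both subgroup means is an arithmetic impossibility.** It is not. Different cut-offs can produce it, and a pooled Kaplan-Meier mean need not equal a weighted subgroup average.
- **That the patients must be the same 29 and 19.** The 29 are chemotherapy recipients, 42% had radiotherapy, and the comparator is described differently for OS and for DFS. A different patient set is a live explanation.
- **That true mean survival can be extrapolated.** A constant hazard fitted to 91.75 gives 1/h = 173 months, but it also gives a median of 120.2 months and S(130.6) = 0.47, which contradicts the stated 50% floor.
- **That more than half the patients were known to be alive.** A Kaplan-Meier estimate is not a count, and 9 of 48 were lost.

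**Conclusion.** The point holds as one that should be fixed. Two conclusions are firm because they follow from the printed text: the overall OS and DFS figures are restricted means with no stated horizon, and the printed OS interval excludes its own estimate. That 8.32 is the SE, with an upper limit near 108.06, is an inference, but an exact one numerically.

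The overall OS mean is 3.65 months above the higher subgroup mean. The 3.86-month gap to the weighted average also assumes a 29:19 split. Different horizons, a different patient set and a misprint all remain possible, and the documents cannot say which. Restriction of the subgroup means is itself inferred, since the text does not say whether those curves stayed above 50%.

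The 46-49 and 85-86 month figures rest on assumed plateaus of 0.50-0.65 and an assumed 130.6-month horizon. They show sensitivity to the cut-off and do not estimate this cohort's survival. A reader might infer that the finding of similar survival with and without adjuvant therapy, or of no significant timing effect, is overturned. Nothing in the documents shows that.

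**What to change.** 1. Report Kaplan-Meier OS and DFS at fixed times, for example 3 and 5 years, with 95% CI and numbers at risk. Do this for the whole cohort, the three timing groups and the adjuvant groups, wherever a group's follow-up reaches that time.
2. If a mean is kept, call it a restricted mean, state the horizon, and use one horizon that every compared group reaches.
3. Re-run the three OS means on one stated patient set, print the group sizes, and either reconcile the means or explain the difference.
4. Correct the overall OS interval.

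The cost is a re-run on existing data and some rewording. The downside is that the headline becomes a percentage, or a restricted mean smaller than 91.75 months. The 5-year figure may be unavailable or very imprecise for the late group of 6 patients.
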